4.1 OVERALL DESIGN

An overview of the study design is provided in Figure 1.

Study BP41316 is a multicenter, randomized, double-blind, parallel-group, 3-arm, placebo-controlled, 12-week treatment Phase II study to investigate the efficacy, safety and tolerability, and pharmacokinetics of RO7017773 in participants aged 15 to 45 years with a diagnosis of ASD and a Wechsler Abbreviated Scale of Intelligence, Second Edition (WASI-II) score of ≥ 50.

Approximately 105 participants with ASD (in order to have at least 84 evaluable participants at study end) aged 15 to 45 years will be enrolled into the study. Participants will be randomized in a 1:1:1 ratio (35 participants randomized to each treatment arm).

After approximately 18 high-functioning (WASI-II ≥70) adults (aged 18 to 45 years) have completed 6 weeks of treatment

the IMC, together with the

SOC will conduct a PK, safety, and tolerability review. Once adequate PK, safety, and tolerability in high-functioning adults have been established and PK-model predictions from healthy adult volunteers are confirmed to be comparable with the PK results in high-functioning adults, then low-functioning adults ([LFAs]; WASI-II ≥ 50 to 69) and adolescents aged 15 to 17 years (both high- and low-functioning) will be included in the study.

A second IMC + SOC review will be performed to evaluate PK, safety, and tolerability data from all available participants once at least 12 adolescents have completed 2 weeks of treatment. Details are provided in Section 4.1.3 and Section 6.3.1.

Randomization will take place on Day 1 after a screening period of at least 2 to up to 4 weeks, and after a pre-baseline and a baseline visit as indicated in the SoA.

Randomization to the different treatment arms will be stratified by age and IQ.

Each participant will be evaluated using several scales and tests at each visit at the clinic. A total of 9 clinic visits (screening period included) and 1 phone contact, to assess for any clinically significant symptoms and/or new medication, are planned (see Section 1.3). In addition, digital biomarker data will be collected from all participants.

Each participant will need a reliable caregiver, parent, or support person who will oversee the participant's adherence with protocol-specified procedures and provide feedback on all informant- based assessments throughout the study. The same support person must attend all on-site visits. For support persons of high-functioning adult participants, no on-site visits are necessary after the screening visit if the support persons opt to complete all electronic clinical outcome assessments (eCOA), interview, and forms remotely (see Appendix 1 Section 2.1.2.2).

Interim analyses will be performed as outlined in Section 9.5.

4.1.1 Length of the Study

The total duration of the study for each participant will be up to 24 weeks (approximately 5.6 months), divided as follows:

- Screening period of at least 2 weeks and up to 4 weeks
- Study pre-baseline and baseline period (2 weeks)
- Study treatment period with fixed dose (12 weeks)
- Safety and efficacy follow-up period (6 weeks).

4.1.2 Individual Stopping Criteria

Dosing will be stopped at any time during the study in a given individual participant if one of the following circumstances occurs, unless it is determined by the Investigator that the occurrence is not related to the administration of the study drug:

- QTc: A confirmed QTcF (average of triplicate values) above 480 ms or a change from baseline by more than 60 ms (when confirmed in repeat measurement within 30 minutes), will result in drug interruption. For the assessment of the QTcF stopping rule, central ECG readings should be used to determine whether the criteria have been met. An expedited review by the central vendor should be requested by the Investigator to ensure that the results are available before the next administration of the study drug. If the central readings are not available at the time of next dosing, this stopping criterion will apply. Study drug may be resumed with the joint agreement of the Investigator and the Sponsor's Medical Monitor when follow-up test results show that the participant no longer meets the dose interruption criteria.
- **Liver safety:** Any participant with the occurrence of either of the following liver values will be discontinued:
 - ALT or AST >3 x ULN and bilirubin >2 x ULN
 - ALT or AST >3 x ULN associated with symptoms (new or worsening) believed to be related to liver injury or hypersensitivity
- Other findings which, at the joint discretion of the Sponsor's Medical Monitor, the Sponsor Safety Science Leader and the Investigator, indicate that dosing in this individual should be stopped (e.g., severe sedation/somnolence, cognitive impairment) (see also Table 10).

Ultimately and in case of disagreement, the Investigator remains responsible for the decision to stop dosing.

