In addition, the protocol includes a stopping rule for dosing when QTcF measurement exceeds a limit of 480 ms confirmed in repeat measurement within 30 minutes (see Section 4.1.2). This criterion has been set to a more conservative value than typically used in clinical trials (i.e., 500 ms) as per ICH Topic E14 (Section 2.1.2. Safety Monitoring, and Discontinuation Criteria). The rationale for this lower threshold for discontinuation is based on the assessment of risk-tolerance level in this trial: although the potential for RO7017773 to increase QTc is not expected at the doses used in BP41316, participants with ASD are likely to use concomitant medications such as antipsychotics with a potential effect of QTc prolongation. With a stopping rule fixed at 480 ms, the Sponsor has fixed the QTc inclusion criterion to a maximum of 450 ms irrespective of sex in order to have a margin between the inclusion threshold and the stopping criterion.

In summary, RO7017773 has the potential of improving social communication and repetitive and restricted behaviors in individuals with ASD. Safety and tolerability in healthy volunteers did not reveal a drug-associated safety pattern considered prohibitive for Study BP41316. Safety monitoring will focus on AE reporting, cardiovascular and laboratory parameters. Also included are assessments of somnolence, sleep propensity, cognition, anxiety, and suicidality. Safety monitoring will be supplemented by stopping rules for individual participants (see Section 4.1.2) and assessed on predefined timepoints or on an ad hoc basis by an IMC and SOC (see Section 4.1.3). Upon review of data by the IMC and SOC and if no safety signal is observed in the initial highfunctioning adult participants, the enrollment of the (high- and low-functioning) adolescents and low-functioning adults will start. On the basis of the neurodevelopmental nature of the disorder, the mechanism of action, the observed clinical safety and tolerability, and the potential of RO7017773 to address a large unmet need in individuals with ASD, the risk-benefit ratio is deemed acceptable for the clinical development of RO7017773, also taking into account that the study will include participants with intellectual disabilities and participants younger than 18 years of age.

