- 5. Risk of suicidal behavior in the opinion of a certified clinician or as evidenced by a "yes" to questions 4 and/or 5 of Columbia-Suicide-Severity Rating Scale (C-SSRS) taken at screening and baseline with respect to the last 12 months or period since the screening visit, respectively, or any suicide attempt in the past 5 years.
- 6. Unstable epilepsy/seizure disorder within the past 6 months.

Cardiovascular conditions

- 7. Concurrent cardiovascular disease considered not well controlled by drug treatment, including participants with clinically significant bradycardia and arrhythmias, myocardial infarction within 12 months of screening or uncompensated heart failure.
- Confirmed clinically significant abnormality on 12-lead electrocardiogram (ECG), including a QTcF of ≥450 ms (based on the average of 3 consecutive measurements). Central ECG readings should be used to determine if this criterion is met.
- 9. Congenital heart diseases not treated and congenital QTc prolongation or family history of Long QT Syndrome.

Other conditions

- 10. Medical history of malignancy if not considered cured or if occurred within the last 3 years with the exception of fully excised non-melanoma skin cancers or in-situ carcinoma of the cervix that has been successfully treated.
- 11. Concomitant disease, condition or treatment which would either interfere with the conduct of the study or pose an unacceptable risk to the participant in the opinion of the Investigator

12. Known active or uncontrolled bacterial, viral, or other infection (excluding fungal infections of nail beds) or any major episode of infection or hospitalization (relating to the completion of the course of antibiotics) within 6 weeks prior to the start of drug administration.

Prior/Concomitant Therapy

13. Use of prohibited medications or herbal remedies (with the exception of herbal remedies approved by the Medical Monitor or designee) within 6 weeks or 5 half-lives (t_{1/2}) prior to randomization (whichever is longer).

Prior/Concurrent Clinical Study Experience

- 14. Donation or loss of blood over 500 mL in adults and 250 mL in adolescents within 3 months prior to randomization.
- 15. Participation in an investigational drug study within 1 month or 5 times the t_{1/2} of the investigational molecule (whichever is longer) prior to randomization or participation in a study testing an investigational medical device within 1 month prior to randomization or if the device is still active.

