6.5.1 Permitted Therapy

Participants must be on a stable prescribed medication regimen for 8 weeks before screening, with the exception of antipsychotic therapies and antiepileptic treatments (where participants need to be on a stable regimen for at least 12 weeks and 6 months before screening, respectively; see inclusion criterion 12 in Section 5.1). Any stable prescribed medication at screening should remain stable throughout the study. All changes in prescribed medication need to be discussed with the Sponsor (Medical Monitor or designee).

Examples of Allowed Medications:

- Selective serotonin reuptake inhibitor/serotonin-norepinephrine reuptake inhibitor (SSRI/SNRI) antidepressants including fluoxetine (see also inclusion criterion in Section 5.1)
- Melatonin
- Trazodone (at low doses) for insomnia
- Aripiprazole
- Risperidone
- Psychostimulants (e.g., methylphenidate)
- Clonidine
- Occasional use of paracetamol/acetaminophen
- Antiepileptic medication (except carbamazepine and phenytoin, which are prohibited because of CYP3A induction) must be stable for 6 months (see also inclusion criterion 12 in Section 5.1)

- Benzodiazepines with a short $t_{1/2}$ (e.g., lorazepam, alprazolam, or oxazepam) are allowed if
 - taken only on an as needed (PRN) basis,
 - limited to 3 times per week,
 - prescribed for short-term or intermittent medical conditions and,
 - not taken immediately before the assessments visits (i.e., not within 2 days or within 5 times the elimination t_{1/2}, whichever is longer before a scheduled visit).

Note: for benzodiazepines with a long $t_{1/2}$ (except for benzodiazepines to treat emerging symptoms of rebound and/or withdrawal effects) see Section 6.5.3.

- Drugs known to prolong QTc interval will be allowed if stable at screening provided the screening QTc does not meets exclusion QTc criterion (see list of drugs known to prolong QTc in Appendix 8).
- Any medication for medical illnesses other than ASD not listed under prohibited medications
- Vaccines, including those against COVID-19

Any other medications require the approval from the Investigator and the Sponsor's Medical Monitor (or designee).

Participants who use oral contraceptives, hormone-replacement therapy, or other maintenance therapy should continue their use.

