Suicidal risk	In case of treatment-emergent suicidal risks, complete the C-SSRS and consider further evaluation and clinical management (e.g., immediate referral to mental health services and patient safety precautions)				

Table 10 Guidelines for Managing Specific Events (cont.)

Type of Risk	Risk Mitigation
Withdrawal/rebound effects	 Depending on the severity, consider surveillance and symptomatic treatment (e.g., midazolam, diazepam, melatonin, and trazodone)
	 In case of emerging symptoms of rebound and/or withdrawal effects of the study drug during the follow- up period after end of treatment at Week 12, treatment with benzodiazepines is allowed (if possible after discussion with the Sponsor).
	Seizures; Handling of seizures should follow the recommendation by the International League against Epilepsy (https://journals.sagepub.com/doi/10.5698/1535-7597-16.1.48):
	 In case of participants with a first seizure, the local emergency doctor should be called; the diagnostic workup as well as the treatment will depend on the type and duration of the seizure.
	 In case of participants with known seizures, the emergency medication (typically, intramuscular midazolam, intravenous (IV) lorazepam, or IV diazepam) should be given after 3 to 5 minutes (as per local recommendation).
Paradoxical reactions	Depending upon severity, consider symptomatic treatment; if necessary take the advice of an emergency physician (treatment option: e.g., blood pressure management, physostigmine, flumazenil, and haloperidol)
	 If a participant experiences a paradoxical reaction, anxiety, or mood agitation, treatment must be paused and can be restarted only after discussion with the Sponsor.
Overdose with exacerbated CNS effects	 In cases of exacerbated symptoms of sedation, coma, or respiratory depression, consult an emergency physician and apply symptomatic treatment (e.g., blood pressure and airway management, flumazenil).
QTc Prolongation	QTcF (average of triplicate values) >480 msec or a change from baseline of >60 ms (when confirmed in repeat measurement within 30 minutes and based on central reading): stop dosing (see also stopping rules in Section 4.1.2)
	 If the QTcF does not normalize after interruption of the study drug and a washout period of 1 week, the participant should receive appropriate emergent treatment and be referred to a cardiologist for evaluation.

Table 10 Guidelines for Managing Specific Events (cont.)

Type of Risk	Risk Mitigation

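### Section 4.1.2 lets the Investigator alone waive the QTc interruption by judging the event unrelated to study drug, which fits poorly with the rest of the QTc rule

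*Protocol*

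**What the plan says.** **The rule.** Protocol Section 4.1.2 lists circumstances in which an individual's dosing is stopped, "unless it is determined by the Investigator that the occurrence is not related to the administration of the study drug". QTc is the first bullet. The triggers are a confirmed QTcF above 480 ms or a change from baseline above 60 ms, and the stated consequence is interruption of study drug. The bullet also applies the stop when the central reading has not arrived by the next dose. Resumption needs the Investigator and the Medical Monitor to agree, and only "when follow-up test results show that the participant no longer meets the dose interruption criteria". The section closes by leaving the stopping decision with the Investigator if opinions differ.

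**The other statements of it.** The QTc row of Table 10 (Section 8.3.7.2) gives the same two limits, "when confirmed in repeat measurement within 30 minutes and based on central reading): stop dosing (see also stopping rules in Section 4.1.2". Section 2.3 describes "a stopping rule for dosing when QTcF measurement exceeds a limit of 480 ms confirmed in repeat measurement within 30 minutes". Neither mentions relatedness; both refer the reader to Section 4.1.2.

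**The reason for 480 ms.** Section 2.3 explains why the limit is below the usual 500 ms: "participants with ASD are likely to use concomitant medications such as antipsychotics with a potential effect of QTc prolongation". It adds that the study drug is not expected to prolong QTc at the study doses.

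**Co-medication and entry.** Section 6.5.1 states: "Drugs known to prolong QTc interval will be allowed if stable at screening". Section 5.2 excludes a clinically significant ECG abnormality, "including a QTcF of ≥450 ms (based on the average of 3 consecutive measurements").

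**The concern.** A participant on an antipsychotic reaches a confirmed QTcF above 480 ms. The Investigator has been told that the study drug is not expected to prolong QTc, and a more obvious culprit is on the medication list. Attributing the finding to the antipsychotic is a natural step, and under Section 4.1.2 as written a determination of non-relatedness means that dosing need not stop. Yet likely co-medication of this kind is the reason given for lowering the limit to 480 ms.

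At stake is continued dosing with an investigational drug after a confirmed cardiac exceedance, in a trial that includes adolescents and participants with intellectual disability. One later safeguard would also drop out. The cardiology referral in Table 10 starts from an interruption followed by a one-week washout, so it is not triggered if dosing never stops.

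**Working it through.** This is mainly a comparison of texts; the plan gives no figure to reproduce.

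**Scope of the exception.** It stands before the list, so it governs every bullet, including QTc. Nothing in the QTc bullet disapplies it.

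**Side by side.**

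| Place | Limits | Consequence | Relatedness exception |
|---|---|---|---|
| 4.1.2 lead-in | none | stop | yes, Investigator alone |
| 4.1.2 QTc bullet | 480 ms; 60 ms change | interruption | none of its own; governed by the lead-in |
| Table 10, QTc row | 480 ms; 60 ms change | stop | not stated; refers to 4.1.2 |
| Section 2.3 | 480 ms | stop | not stated; refers to 4.1.2 |

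**Which text governs.** Section 7.1 lists among the reasons for discontinuation any event meeting the criteria defined in Section 4.1.2. With the two cross-references, this makes Section 4.1.2 the defining text, so the exception is operative.

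**Asymmetry within 4.1.2.** Restarting after an interruption takes two parties and a resolved ECG. Not interrupting at all takes one party and a causality judgment. A missing central reading halts dosing by default, while a confirmed exceedance judged unrelated does not.

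**Reach of the Section 2.3 rationale.** It explains the 480 ms limit only. It gives no reason for the 60 ms change criterion, so that part of the argument does not extend to it.

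**How narrow the route is.** Entry requires QTcF below 450 ms, so crossing 480 ms means a rise of more than 480 − 450 = 30 ms from the screening value. With unchanged co-medication that is less likely to be the co-medication's doing. A drug started or changed during the study is more plausible; Section 8.3.7.1 foresees this and asks for an extra triplicate ECG.

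**Cost of interrupting (SAP Section 3).** Week 12 efficacy data are excluded if overall compliance is below 60%, or if more than 7 consecutive doses are missed immediately before the assessment. Assume a constant number of doses per day over 84 days:

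- Limit: 0.60 × 84 = 50.4 dosing days.
- 33 days missed: 51/84 = 60.7%, kept if the 7-dose condition is also met.
- 34 days missed: 50/84 = 59.5%, excluded.
- Permanent stop at Day 14: 14/84 = 16.7%, excluded.
- Evaluable per arm: 84/3 = 28, so one loss is 1/28 = 3.6%. The plan already allows for 35 − 28 = 7 losses per arm.

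**The case against.** The strongest reply is that this is a deliberate choice, well surrounded by safeguards. Much of that stands.

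- *Hierarchy.* A reader might infer that the protocol contradicts itself and leaves sites no way to tell which text prevails. The documents do not support that: Section 7.1 and both cross-references point to Section 4.1.2, and Table 10 is headed as guidelines. The liver row of Table 10 likewise omits the exception although the same lead-in covers the liver bullet, so the table may simply be abbreviating.
- *Causality.* A reader might infer that the mere presence of a QTc-prolonging drug licenses the waiver. It does not. The default is to stop, and Appendix 2, Section 3.2 makes co-medication one consideration among several, with timing, course and known associations. An event to which study drug may have contributed is not thereby unrelated.
- *Isolation.* A reader might picture a blinded Investigator deciding unseen. Section 8 asks for immediate Sponsor discussion of urgent safety concerns. Section 8.3.7.2 has the site evaluate the participant promptly and contact the Medical Monitor. Section 8.3.6 and Appendix 2 require 24-hour reporting regardless of relationship. Section 6.3.2 permits unblinding in the participant's interest. Sections 2.3 and 4.1.3.1 provide ad hoc review by an unblinded IMC and SOC.
- *Monitoring gap.* Scheduled ECGs after Day 14 resume at Day 84, 70 days later (56 to 84 with the visit windows). That is not an expected gap after an exceedance, because Section 8.3.7.2 prompts an unscheduled evaluation.
- *Redaction.* Much of the nonclinical and clinical safety background is blacked out, and a rationale may lie there.

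What remains is that none of these provisions makes interruption mandatory, and Section 4.1.2 leaves the last word with the Investigator.

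**Conclusion.** The point holds as a weakness in the governing text. Section 4.1.2 lets one person waive the QTc interruption on a judgment of non-relatedness. That fits poorly with the bullet's mandatory consequence, the Table 10 wording and the two-party resumption rule. For the 480 ms limit, it also fits poorly with the reason the limit was lowered. The practical route is narrow and several safeguards surround it, so the severity is minor to moderate.

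The size cannot be stated as a number of participants: the documents give neither how many will take QTc-prolonging drugs nor how many exceedances to expect. The 30 ms margin describes the rule; it does not measure harm. The conclusion rests on reading the lead-in as covering every bullet, and on no redacted passage disapplying it for QTc.

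**What to change.** Add to the QTc bullet in Section 4.1.2:

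*The relatedness exception above does not apply to this criterion. Any confirmed QTcF above 480 ms, or change from baseline above 60 ms, interrupts study drug whatever the presumed cause.*

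Keep the present resumption rule. Table 10 and Section 2.3 then agree with Section 4.1.2 unchanged. The other bullets are outside this point.

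The cost is some extra interruptions, including on placebo. If a QTcF driven by co-medication does not fall below the limits, the interruption becomes permanent. Adjusting the co-medication is possible, but Section 6.5.1 says: "All changes in prescribed medication need to be discussed with the Sponsor". On the dosing assumption above, a temporary interruption of up to 33 days need not cost the Week 12 data. A permanent stop generally does, at about 1 of 28 evaluable participants in that arm.

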4.1.3 Administrative Structure

4.1.3.1 Internal Monitoring Committee (IMC) and Scientific Oversight Committee (SOC)

An IMC consisting of a selected subset of Roche representative(s) as identified in the "IMC Agreement" will be responsible to perform interim analyses of accumulated safety, tolerability, PK, and efficacy (as required) data. The IMC members, the clinical

pharmacologist, and the pharmacometrician will be unblinded to individual study treatment allocation (see Section 6.3 for treatment allocation and blinding of data).

An SOC consisting of at least one external expert will support the IMC in making their recommendations. These SOC members will likewise be unblinded to individual study treatment allocation.

Access to treatment assignment information will follow the Sponsor's standard procedures (see Section 6.3).

On the basis of accumulated study data available at their review, the IMC and SOC may recommend adjustment(s) of the dose levels, dosing regimen, or the timing of dosing (see Section 6.6).

Further details can be found in the "IMC Agreement" and in Section 9.5 (Interim Analyses).

